## **Data collection, management, and analysis**

### **Data collection methods**

Assessments will be conducted in standardized conditions, in a clinical setting, in a calm and comfortable environment, in small groups, and performed by a qualified exercise professional. The assessments will be conducted in the morning, starting with the body composition measurements, followed by a 15-minute pause so participants can eat (since they will be weighted while fasting), preceded by a 10-minute warm-up with general movements to mobilize big muscle groups and the physical tests, that will be performed in the following order: shoulder angular measurements, strength, mobility, and aerobic endurance. Participants will be divided into small groups to facilitate instruction and conduction of the tests. Participants will receive the accelerometers one week before

the field tests and return them on the physical assessment day. After the field measurements, all questionnaires will be delivered and answered through email (Google Forms). Summarized information regarding assessment time points and tools can be found in Table 1.

### **Primary outcome**

**Chemotherapy completion rates.** Chemotherapy completion rates will be assessed at  $T_0$ ,  $T_1$ , and  $T_2$ . This outcome will be reported as the mean RDI ( $\text{mg} \cdot \text{m}^{-2} / \text{wk}^{-1}$ ), which corresponds to a fraction of the planned chemotherapy dose intensity, by dividing the dose of chemotherapy per square meter (of surface area where the drug is related) in each cycle by the number of weeks in a cycle . Information regarding the planned chemotherapy treatment and the effectively received treatment (i.e., dose, type, and duration) will be acquired from medical records after signing the informed consent . A successful chemotherapy completion rate will be considered if the RDI is  $\geq 85\%$  of the planned treatment, as an RDI below this cut-off is associated with a worse disease prognosis and lower treatment efficacy . Calculations to compare the actual chemotherapy dose intensity received and the initially planned dose intensity will be calculated as total milligrams of chemotherapy divided by the product of the body surface (in square meters) and total weeks of treatment . The RDI results from the actual dose intensity received are divided by the planned dose intensity .

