Some evidence has shown that exercise may modulate treatment response through its effects on the tumor and may also improve the tolerability of chemotherapy, making it a potential tool to enhance chemotherapy completion rate (i.e., reception of the planned treatment doses) . So far, evidence shows that exercise does not disrupt chemotherapy delivery, but failed to demonstrate that exercise may increase chemotherapy completion rates . For instance, Mijwel et al. (2020) randomized 240 women to either a resistance and high-interval training group, aerobic and high-interval training group, or usual care groups and found no effects of exercise on chemotherapy completion rate. Sanft et al. (2023) conducted a home-based exercise and nutrition counseling intervention on 173 women with BC undergoing chemotherapy, reporting no intervention effects in RDI compared to the usual care group.

Home-based exercise interventions (i.e., programs performed inside or in the immediate surroundings of one's home ) are a convenient and flexible strategy with high adherence and proven to be effective and beneficial to improve functional

performance, raising activity levels, reducing symptoms, and improving overall quality of life in women with a BC diagnosis .

The need for a pleasant and sustainable exercise practice may be a relevant topic when considering the psychological and physiological burden and stress that often accompanies women after a BC diagnosis and during the treatment phase when dealing with therapy side effects . Even though some evidence suggests that allowing self-selection of exercise intensity may not be optimal to maximize health or fitness, increasing enjoyment and adherence to exercise practice and creating sustained lifestyle changes can be more beneficial . Although some exercise methods might be highly efficient in potentiating physiological outcomes in women with BC (e.g., high-intensity interval training), they may fail to meet this population's preferences and hinder the sustainability of active lifestyle behaviors after the studies' interventions .

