### **Outcomes**

Assessments will be performed at four-time points: baseline ( $T_0$ , 1-2 weeks post-chemotherapy start), mid-treatment ( $T_1$ , planned mid-cycle), post-intervention ( $T_2$ , 3-4 weeks post-chemotherapy finishing), and 3 months post-intervention finishing ( $T_3$ , follow-up). The primary outcome of this study will be the chemotherapy completion rates. Secondary outcomes will include functional performance, body composition, PA levels, sedentary behavior (SB) (i.e., behaviors with energy expenditure  $\leq 1.5$  METs while sitting, or lying ), and quality of life. Demographical information (age, education level, marital status, socioeconomic status), PA history, and clinical history data (disease and treatment history, concomitant comorbidities, and other existing health problems besides BC) will also be collected as covariates in the data analysis.

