### **Statistical methods**

All data will be analyzed using IBM SPSS (version 29.0). Factorial ANCOVAs with repeated measures will be used for the primary and secondary outcomes, adjusted for potential covariates (e.g., concomitant treatments, BC diagnosis, neo-adjuvant/adjuvant chemotherapy). Independent sample T-tests will be used to compare results between groups at each time point, considering chemotherapy completers versus non-completers . A Fisher's exact test will compare the proportion of participants who needed chemotherapy adjustments from those who did not . The intention-to-treat analysis will be conducted to ensure that all participants are included in the overall assessment, considering their compliance with the study protocol. The Last Observation

Carried Forward method will be used to input missing data values. A per-protocol analysis will also be conducted without participants who failed to complete at least 50% of the training sessions. Normality plots and Kolmogorov-Smirnov tests will be performed to test the normality of outcome variables. If normality is not satisfied, non-parametric tests will be applied (e.g., Krustal-Wallis). Mediators of change (i.e., mechanisms by which RDI) will be explored using structural equation modeling (AMOS 18.0) and multiple mediation analysis (PROCESS macro for SPSS). Putative candidates will include treatment (e.g., dose planned vs. given dose, planned cycles minimum/maximum, treatment interruption ratios, response to treatment, percentage of participants who needed dose adjustments, and the mean value of dose adjustment), and physiological (e.g., body composition, functional performance, handgrip strength, PA levels) variables. Mediation occurs when a causal effect of an independent variable occurs on a dependent variable, partly or entirely explained by a mediator. Indirect effects testing will be performed using Preacher and Hayes' procedures.

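### The RDI formula does not say which weeks divide the received dose; on the likelier reading, an on-time early stop with equal full-dose cycles scores 100% and counts as success

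*Protocol*

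**What the plan says.** The Primary outcome section of the Protocol gives the formula for the primary endpoint. Dose intensity is "calculated as total milligrams of chemotherapy divided by the product of the body surface (in square meters) and total weeks of treatment", and the ratio is then formed: "The RDI results from the actual dose intensity received are divided by the planned dose intensity". The section does not say whether the weeks in the received term are those that elapsed or those that were planned. It has no rule for planned cycles that were never given.

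Two features lean towards elapsed weeks. The section contrasts an actual intensity with a planned one, and it collects from the medical records "the effectively received treatment (i.e., dose, type, and duration", so the received duration is available. In the Outcomes section, T2 is timed at "3-4 weeks post-chemotherapy finishing", that is, from when chemotherapy actually ends.

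The same section also describes the outcome per cycle, dividing the dose per square metre "in each cycle by the number of weeks in a cycle". It does not say whether an omitted cycle enters as zero.

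The success rule follows: "A successful chemotherapy completion rate will be considered if the RDI is" at least 85% of plan. The Background and rationale section explains the concept as "chemotherapy completion rate (i.e., reception of the planned treatment doses". The Statistical methods section adds t-tests "considering chemotherapy completers versus non-completers".

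**The concern.** Completion, as the Background explains it, means receiving the planned doses. An endpoint with that name should score a woman who stops halfway lower than one who finishes. If the received dose is divided by the weeks she was actually treated, stopping early removes dose and weeks in the same proportion, and the ratio does not move.

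This affects the primary endpoint as a mean, and the 85% success rule. It probably also affects the completer split in the Statistical methods section, although the Protocol does not say that the split uses the 85% cut-off. On the elapsed-weeks reading the order of two patients can be reversed: one who stops on time at the halfway point passes, while one who receives every cycle with a four-week delay fails. If exercise helped women continue rather than stop, such scoring could hide the benefit.

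**Working it through.** The Protocol states no RDI value to reproduce, so the check is algebra on its formula.

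**Inputs from the Protocol:** dose intensity = total mg / (body surface × weeks); RDI = received intensity / planned intensity; success if RDI is at least 85%.

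**Assumptions, not in the Protocol:** equal cycles of 3 weeks, full dose D (per m²) in each cycle given, constant body surface, and the last given cycle counted at its full length. These are for illustration only.

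**Elapsed weeks, on-time early stop.** With k of C cycles of length c: RDI = (kD / kc) / (CD / Cc) = (D/c) / (D/c) = 1 for every k and C. The 100% does not depend on the 3-week figure.

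**Planned weeks in both terms.** The weeks cancel: RDI = kD / CD = k/C, whatever the delay.

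**Six planned cycles, 18 planned weeks:**

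| Course received | Elapsed weeks | RDI, elapsed | RDI, planned |
|---|---|---|---|
| 3 of 6, on time | 9 | (3/9)/(6/18) = 100% | 3/6 = 50% |
| 3 of 6, 1-week delay | 10 | (3/10)/(6/18) = 90% | 50% |
| 3 of 6, 3-week delay | 12 | (3/12)/(6/18) = 75% | 50% |
| 5 of 6, one skipped mid-course, calendar kept | 18 | (5/18)/(6/18) = 83.3% | 83.3% |
| 6 of 6, 3-week delay | 21 | 18/21 = 85.7% | 100% |
| 6 of 6, 4-week delay | 22 | 18/22 = 81.8% | 100% |
| 6 of 6, 6-week delay | 24 | 18/24 = 75% | 100% |

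**When the class at 85% is affected.** On elapsed weeks, an on-time stop passes although the share of planned cycles received is below 0.85 at all 3 possible stop points of 4 planned cycles, all 5 of 6 (5/6 = 0.833), and 6 of the 7 for 8 planned cycles (7/8 = 0.875 passes either way). For a full 18-week course, the two readings disagree once elapsed time exceeds 18/0.85 = 21.2 weeks.

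**Sensitivity to the last-cycle convention.** If weeks ran only from first to last dose, an on-time stop after 4 of 6 would give (4/9)/(6/15) = 111%. The direction of the problem is unchanged.

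**The case against.** Four points can be made on the other side.

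- **Omitted cycles are not generally missed.** A reader might infer that the formula misses every omitted cycle. It does not: on elapsed weeks, a cycle skipped mid-course with the calendar kept lowers RDI to 83.3% in the example. The gap is confined to cycles dropped at the end. This objection stands and limits the point.
- **The planned-weeks reading is weak.** If planned weeks were used in both terms, the received duration would play no part in RDI, which sits badly with a text that speaks of actual intensity. A reader might infer that the Protocol is evenly split between the readings; the wording does not support that. It leans towards elapsed weeks without fixing them, so the missed-delay problem is the secondary one.
- **The detail may sit in an analysis plan or a cited source.** Neither is available here. But the Protocol itself writes out the primary-endpoint formula, and following its likelier reading conflicts with its own account of completion. That is more than an absent detail.
- **Other analyses may show the problem.** The Fisher test on treatment adjustments and the mediator candidates, which include planned against given dose, may reveal some early stopping. They are separate analyses and do not change how the primary endpoint is scored.

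The exact 100% also needs equal cycles. If dose intensity differs between cycles, an early stop can score above or below 100%.

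**Conclusion.** The point holds for early stopping on the elapsed-weeks reading and should be fixed. With equal cycles and the last given cycle counted at full length, any on-time, full-dose early stop scores 100% and counts as success. In the example of 3 of 6 cycles, half the planned dose was received. The less supported planned-weeks reading fails the other way, because delays never lower RDI.

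A reader might infer that the trial's result would be biased by a known amount or in a known direction. The documents do not support that: they give no rate of early stopping or delay, overall or by arm, so the trial-level effect is unknown. Nor does every case change class: 7 of 8 cycles on time, and a full 18-week course stretched to 21 weeks, pass on either reading.

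**What to change.** Replace the two descriptions in the Primary outcome section with one rule:

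RDI = [total mg/m² received / treatment weeks] / [total planned mg/m² / planned weeks]

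- Treatment weeks = time from first dose to last dose given, plus one planned cycle length, plus the planned length of any cycles dropped after the last dose given.
- Cycles not given count as zero dose. A cycle skipped mid-course adds no extra weeks, because its calendar time is already counted.
- At T0 and T1, apply the same rule only to the part of the planned course scheduled up to that time point, so that a woman on schedule scores 100%. For example, with 3 of 6 cycles scheduled and given by T1: (3/9)/(3/9) = 100%.
- Apply the 85% success rule at T2.

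Checks with illustrative 3-week cycles:

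- 3 of 6 on time: weeks = 9 + 9 = 18; (3/18)/(6/18) = 50%.
- 6 of 6 in 24 instead of 18 weeks: (6/24)/(6/18) = 75%.
- 4 of 6 with a 2-week delay: weeks = 14 + 6 = 20; (4/20)/(6/18) = 60%.
- 7 of 8, one skipped, 24 weeks kept: (7/24)/(8/24) = 87.5%.

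The third check shows why dropped cycles are added to elapsed weeks. Taking the longer of planned and elapsed weeks would give (4/18)/(6/18) = 66.7% and lose the delay.

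The cost is one paragraph of wording. Dose and duration, planned and received, are already collected. Mean RDI and the success rate may look somewhat lower. The rule should be fixed before outcome data are seen, so that the reading cannot be chosen afterwards.

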## Introduction

### Background and rationale

Breast cancer (BC) is the most diagnosed cancer type, with high levels of incidence, prevalence, and cancer-related deaths among women worldwide .

Chemotherapy is commonly used as an anticancer therapy, consisting of the intravenous administration of a combination of cytotoxic drugs to delay cancer growth or, in some cases, eradicate the tumor and prevent cancer cell multiplication, invasion, and metastasizing . However, since chemotherapy drugs are not selective to tumor cells or normal cells, many side effects hinder functional performance (i.e., a person's ability to perform daily activities involving physical effort with vigor and without excessive fatigue) of women with BC . Another problem that may arise during treatment is the development of tumor cells' resistance to chemotherapy, ultimately leading to treatment failure . A relative dose intensity (RDI) (i.e., the dose of drugs delivered to a person with cancer each week of treatment) <85% is associated with a worse disease prognosis and lower treatment efficacy .

Exercise appears to be a safe and effective cancer co-therapy that improves functional performance in women with BC during treatments and may potentially enhance treatment efficacy . Despite the very well-known benefits of exercise for women with BC, this population often fails to adhere to a more active lifestyle and comply with the recommended physical activity (PA) guidelines due to fatigue, conflicting scheduled commitments, sickness, forgetting appointments, pain, procrastination, and lack of self-discipline, enjoyment or interest .

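### Taken literally, the RDI formula weights each drug by its milligrams; the primary outcome needs a stated per-drug calculation

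*Protocol*

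**What the plan says.** The Outcomes section states: "The primary outcome of this study will be the chemotherapy completion rates". The Primary outcome section turns this into relative dose intensity (RDI): "This outcome will be reported as the mean RDI".

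That section describes the calculation twice. The first description is per cycle and takes a dose per square metre ("of surface area where the drug is related) in each cycle by the number of weeks in a cycle"). The second is the only complete formula. For both the received and the planned treatment, dose intensity is "total milligrams of chemotherapy divided by the product of the body surface (in square meters) and total weeks of treatment". The ratio follows: "The RDI results from the actual dose intensity received are divided by the planned dose intensity". A threshold is then applied: "A successful chemotherapy completion rate will be considered if the RDI is" at least 85% of plan. The Background supports that cut with the statement that an RDI "<85% is associated with a worse disease prognosis and lower treatment efficacy".

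The Background also describes chemotherapy as "consisting of the intravenous administration of a combination of cytotoxic drugs". The eligibility criteria admit any neoadjuvant or adjuvant chemotherapy and name no regimen. No section says that RDI is calculated for each drug, how drugs are combined, or over what the mean RDI is taken (drugs, cycles or women).

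**The concern.** The formula's numerator is one milligram total for chemotherapy as a whole. When a woman has more than one drug, adding their milligrams gives each drug an influence proportional to its milligram amount, not to its place in the treatment plan. The same proportional cut can then move RDI a good deal or hardly at all, depending on which drug is cut.

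This matters because RDI is the primary outcome, carries Hypothesis 1, and defines success at 85%. The Background explains completion as receiving the doses that were planned. A woman who missed one planned drug entirely could be classed as successful, and a woman with a modest cut in the high-milligram drug as unsuccessful. As any regimen is eligible, the same proportional loss could also score differently from one regimen to another.

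**Working it through.** **Inputs.** From the protocol: the dose-intensity formula, the ratio of actual to planned, the 85% cut, and the description of chemotherapy as a combination. Not in the protocol: regimens, drug doses, or any worked RDI value, mean or standard deviation. There is therefore no stated RDI figure to reproduce, and the milligram ratios below are assumptions shown over a range.

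**Step 1: what the formula does.** Let drug i have planned milligrams m_i, and let x_i be the fraction received, with body surface (BSA) and weeks (W) as planned. Then

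pooled RDI = [Σ m_i x_i / (BSA × W)] / [Σ m_i / (BSA × W)] = Σ m_i x_i / Σ m_i.

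This is the mean of the drug-level RDIs x_i, weighted by each drug's share of planned milligrams. The comparator is the unweighted mean of the x_i.

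**Step 2: two drugs, planned milligram ratio r:1.**

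- Smaller drug omitted: r/(1 + r).
- Smaller drug cut by 20%: (r + 0.8)/(1 + r).
- Larger drug cut by 20%: (0.8r + 1)/(1 + r).

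| r | Smaller omitted | Smaller cut 20% | Larger cut 20% |
|---|---|---|---|
| 1 | 50.0% | 90.0% | 90.0% |
| 3 | 75.0% | 95.0% | 85.0% |
| 5 | 83.3% | 96.7% | 83.3% |
| 6 | 85.7% | 97.1% | 82.9% |
| 10 | 90.9% | 98.2% | 81.8% |
| 20 | 95.2% | 99.0% | 81.0% |
| Unweighted per-drug mean, any r | 50% | 90% | 90% |

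**Step 3: when does omission pass the cut?** r/(1 + r) ≥ 0.85 requires r ≥ 0.85/0.15 = 5.67, that is, the omitted drug makes up at most 15% of planned milligrams. Below that ratio, the pooled formula also classes omission as a failure.

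**Step 4: classification at 10:1.** Omitting the smaller drug gives 10/11 = 90.9%, a success. A 20% cut of the larger alone gives (8 + 1)/11 = 81.8%, a failure. The per-drug mean gives (1 + 0)/2 = 50% and (0.8 + 1)/2 = 90%, so both classifications reverse.

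**Step 5: three drugs.** At 1:1:10, omitting either small drug gives 11/12 = 91.7%. At 1:2:4, omitting the smallest gives 6/7 = 85.7%. The per-drug mean is 2/3 = 66.7% in both cases.

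**Step 6: where the methods agree.** If every drug is cut to the same fraction x, both methods give x. If all drugs share a delay at full dose, both give planned weeks over actual weeks. At 1:1 they agree for any pattern of cuts. They differ only for cuts that fall unequally on drugs with unequal milligrams.

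**The case against.** The strongest reply is that pooling is one reading and not a stated rule. The formula can be applied drug by drug, and nothing tells the analyst to add milligrams across drugs. The section speaks of a mean RDI, mentions the drug in the singular, and has dose and type taken from the medical records. It also cites sources for the calculation, which are not available here and may contain a combination rule. This stands in part: the text does not prove that the investigators will pool. It does not remove the point. The mean is not said to be over drugs, the singular wording only qualifies surface area, and the one complete formula uses a single total.

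A second reply is that such detail belongs in a statistical analysis plan. Here, however, the protocol states the formula itself, so a later per-drug rule would have to be reconciled with it.

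Third, the Fisher's exact test in Statistical methods compares women who needed chemotherapy adjustments with those who did not. It would register a selective cut whatever the milligrams. That is useful, but it is a separate comparison and leaves RDI and its 85% classification unchanged.

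Stronger conclusions are tempting and are not supported:

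- A reader might infer that the highest-milligram drug alone decides the outcome. The weighting is proportional, and near 1:1 no drug dominates.
- A reader might infer that most dose loss would be missed. That needs the frequency of selective cuts, which the protocol does not give.
- A reader might infer a biased comparison between arms. Randomisation makes the drug weights alike across arms in expectation.

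**Conclusion.** The point holds as a badly fixed definition of the primary outcome. Followed as written, the formula makes RDI a milligram-weighted mean, and selective cuts can fall on the wrong side of 85%. The size depends on assumed ratios with body surface and weeks unchanged: omission of the smaller of two drugs scores 75% at 3:1, 83.3% at 5:1 and 90.9% at 10:1, and passes only from 5.67:1 upward. What is at stake is the validity and sensitivity of the outcome. This should be fixed before analysis, since choosing a combination rule after seeing the data would leave the primary outcome open to selection. Confidence is moderate, because a per-drug intention remains possible and no regimen is given.

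**What to change.** In the Primary outcome section, replace the single milligram total by a per-drug calculation. For each planned cytotoxic drug, divide received by planned dose intensity. Define the woman's RDI as the unweighted mean of these ratios over all planned drugs, with an omitted drug counted as 0, and apply the 85% cut to that mean. State which weeks apply to each drug when drugs are given in sequence. The pooled value can be kept as a sensitivity analysis if wanted.

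The cost is a change of wording and slightly more calculation per woman. Dose, type and duration are already to be taken from the medical records, so no new data are needed. RDI values and the proportion reaching 85% may come out somewhat lower.

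The unweighted mean has a limit of its own, because it can still mask a moderate cut in one drug. A 30% cut in one of two drugs gives (0.7 + 1)/2 = 85%, and a 45% cut in one of three gives (0.55 + 1 + 1)/3 = 85%; both just pass. The protocol also does not show whether its 85% threshold was derived on such an average.
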